The site principal investigator will be responsible to ensure that all conditions for approval of the study are met and that amendments to the protocol or serious adverse events are also reported to the Human Research Ethics Committee (HREC, or equivalent) as required.

This protocol will also be submitted to the Guardianship Board or similar where this is necessary for legal surrogates to provide informed consent for patient participation. The site principal investigator will be responsible to obtain such approval from the relevant body prior to obtaining legal surrogate consent.

DATA MANAGEMENT

Data collection methods

All study-related data will be collected by trained staff at each study site using a paper source document (case report form) developed by the coordinating centre. Data will then be entered into an internet-based database designed by the CIDMU. Data queries will be automatically generated as they are entered into this database.

Enrolled patients will be followed up to death or 6 months post-enrolment. Data collection will be restricted primarily to those variables necessary to define clinical patient characteristics including: baseline demographics, primary diagnoses, physiological parameters, diagnostic interventions, therapeutic interventions and documentation of deaths, other serious adverse events, and patient outcomes.

Patients and/or their legal surrogate will be asked to provide three possible points of contact (home and close family contact details) to the research staff prior to discharge. Full protocol data will be collected in all patients including those where the study is discontinued prior to the end of the study period. Patients (or a surrogate – generally a close family member) who are alive at 6 months after enrolment will be asked to complete a questionnaire via post or telephone by a trained follow-up assessor from the coordinating centre. This follow-up assessor will use a standardized structured telephone questionnaire⁵² to measure the QOL assessments EQ-5D⁵³ and SF-36v2^{54,55}.

Data variables collected

- Demographic data
- Height
- Weight
- Admission diagnosis
- Cause of ARDS
- Classification of ARDS as diffuse or focal (by an independent radiologist)
- PaO₂/FiO₂ ratio at enrolment
- Barotrauma
- Mode of ventilation
- Ventilation parameters
- ABG results
- Vital signs
- SOFA scores
- Daily fluid balance
- Rescue therapy details
- Co-interventions
- Open lung procedure details
- Ventilation weaning
- Adverse events
- Serious adverse events
- Protocol deviations
- Outcomes – duration of ventilation, length of stay, survival, discharge destination

- Long term outcomes (at 6 months) – SF36, EQ5D, cost-effectiveness analysis

Data management

Data management will be performed by the CIDMU at the Department of Epidemiology and Preventive Medicine, Monash University.

Monitoring

The study will be monitored by a representative of the coordinating centre. Prior to study commencement, a start-up teleconference or visit will be conducted at each site. Monitoring of the data collection and protocol adherence will occur after study completion for the first intervention and control patient at each site.

The database will be developed to routinely report queries and protocol violations. Additional queries will be generated by the Project Manager following regular reviews of the data. Additional on-site monitoring will also be performed if the routine reviews indicate any significant issues at individual sites. Email and telephone communication will supplement site visits.

A monitoring report will be prepared following each visit and reviewed by the management committee. A follow up letter will be sent to the principal investigator and research coordinator at the site and will be filed in the site investigator file.

Medical records, any other relevant source documents and the site investigator files will be required to be made available to the coordinating centre representative for these monitoring visits during the course of the study and at the completion of the study as needed.

The aims of monitoring visits are to:

- a) Check data accuracy by performing source data verification of the electronic case report form against the original source documents
- b) Check for protocol deviations to report these to the Management Committee as necessary
- c) Review primary and secondary outcome data collected for each patient
- d) Confirm the informed consent procedures approved by the site's HREC have been followed and view each original signed consent form
- e) Check data security and access
- f) Review all serious adverse events (SAEs) to allow follow up of all reported SAEs
- g) Review investigator site files for completeness and accuracy
- h) Assist the study staff with any queries or problems they may have in relation to the study

Protocol deviations

A protocol deviation is an unanticipated or unintentional departure from the expected conduct of an approved study that is not consistent with the current research protocol or consent document. A protocol deviation may be an omission, addition or change in any procedure described in the protocol.

Given that investigators are responsible for patient safety and care, they may implement a deviation from, or a change of, the protocol to deal with an immediate hazard to trial patients without prior HREC approval. The implemented deviation or change must be reported in a protocol deviation form. The deviation must be reported by the principal investigator using the case report form so that it can be reported to the coordinating centre and the HREC (if applicable).

STATISTICAL CONSIDERATIONS

Power calculations and sample size

Based on data from the PHARLAP pilot study, with 282 subjects this study will have an 80% power to detect a difference equal to 33% of a standard deviation (equal to 3VFD's) with a two sided p-value of 0.05. To account for likely occurrence that VFD will not follow a normal distribution, the sample size has been inflated by 15% to 324 in accordance with Lehmann⁵⁶. Allowing for up to a 5% rate for withdrawal or loss to long term follow up, 340 patients will be enrolled.

Statistical and analytical plan

Independent senior statisticians at Monash University will perform data analysis. Baseline and outcome variables will be compared using Chi-square tests for categorical variables, Student's t-test for normally distributed continuous variables and Wilcoxon rank-sum tests for non-normally distributed continuous variables. Duration of ventilation will be analysed using Cox-Proportional Hazards regression with deceased patients censored at death, allowing for results to be reported using Kaplan Meier curves. Furthermore, duration of ventilation will be stratified into survivors and non-survivors. If as expected, the duration of ventilation in each strata is well approximated by a log-normal distribution, this will enable log-transformed duration of ventilation to be analysed using parametric analysis (student t-tests) and reported as a ratio (95%CI). If normality cannot be achieved then the data would subsequently be analysed non-parametrically. Should any baseline imbalances be found to exist between groups, additional sensitivity analysis will be performed using Cox Proportional Hazards regression adjusting for imbalanced covariates. All analyses will be intention-to-treat. A complete statistical analysis plan will be finalised prior to study completion.

Interim analysis

One midpoint interim analysis (after primary outcome data is available for 170 patients) will be performed to assess accumulated safety data. This will be reported to the Data Safety Monitoring Committee, but will not be made available to the Management Committee or to study sites.

Subgroup analyses

We plan to compare study outcomes in the following pre-specified subgroups:

- (a) Patients with severe ARDS ($\text{PaO}_2/\text{FiO}_2 < 100$) versus patients with moderate ARDS ($\text{PaO}_2/\text{FiO}_2$ 100-200 mmHg) at enrolment.
- (b) Patients with diffuse ARDS versus patients with focal ARDS at enrolment (determined by independent radiologists).
- (c) Patients who are responders to the open lung strategy versus patients who are non-responders (defined as meeting lack of improvement in static lung compliance definition).

SAFETY OF SUBJECTS

Data Safety Monitoring Committee

An independent Data Safety Monitoring Committee, comprising experts in clinical trials, biostatistics and intensive care will be established. The committee will be responsible for monitoring mortality related to serious adverse events, serious adverse events and reviewing the interim safety analysis.

Adverse events

Adverse events are defined as any untoward medical occurrence in a patient or clinical investigation subject administered an investigational intervention and does not necessarily have to have a causal relationship with this intervention (adapted from the Note for Guidance on Clinical Safety Data Management: Definitions and Standards for Expedited Reporting (CPMP/ICH/377/95 July 2000).

It is recognised that the patient population with critical illness and ARDS will experience a number of common aberrations in laboratory values, signs and symptoms due to the severity of the underlying illness and the impact of standard therapies. These will not necessarily constitute an adverse event unless they require significant intervention or are considered to be of concern in the investigator's clinical judgement.

In all cases, the condition or disease underlying the symptom, sign or laboratory value should be reported e.g. renal failure rather than hyperkalaemia, and agitation rather than self-extubation.

Serious adverse events

Serious Adverse Events (SAE) are defined in accordance with the Note for Guidance on Clinical Safety Data Management: Definitions and Standards for Expedited Reporting (CPMP/ICH/377/95) (July 2000) as any one of the following untoward medical occurrences:

- Results in death
- Is life-threatening
- Requires inpatient hospitalisation or prolongation of existing hospitalisation
- Results in persistent or significant disability/incapacity
- Is a congenital anomaly/birth defect
- Is an important medical event which may require intervention to prevent one of the previously listed outcomes

In this study all SAEs will be reported if they possibly, probably or causally are related to study enrolment. However, consistent with the advice of Cook et al, adverse events already defined and reported as study outcomes (mortality) will not be labelled and reported a second time as serious adverse events.

Reporting of SAEs

Separate case report forms will be developed to record adverse events and serious adverse events.

SAEs which occur from the time of enrolment until day 90 follow-up will be reported to the coordinating centre via the internet-based SAE form. SAEs should be reported to the coordinating centre within 24 hours of study staff becoming aware of the event.

Minimum information to report will include:

- Patient initials and study number
- Nature of the event
- Commencement and cessation of the event

- An investigator's opinion of the relationship between study involvement and the event (unrelated, possibly, probably or definitely related).
- Whether treatment was required for the event and what treatment was administered.

Website address: <https://pharlap.org.au>

Telephone Numbers:

ANZIC-RC: [name]

ANZIC-RC: [name]

Chief investigator: [name]

SAEs must be reported using the study website. The event and report may be discussed with the coordinating centre staff or chief investigator if necessary. Coordinating centre staff will be responsible for following-up SAEs to ensure all details are available. The site principal investigator is responsible for inform the relevant HREC of all SAEs which occur at their site, in accordance with local requirements.

FUNDING

The PHARLAP study is funded by project grants from the National Health and Medical Research Council (NHMRC) (Project grant no APP1021203), the Alfred Hospital, and the Health Research Council of New Zealand. The ANZIC-RC will supply infrastructure and administrative support.

PUBLICATION

The study will be conducted in the name of the PHARLAP investigators, the ANZIC-RC and the Australian and New Zealand Intensive Care Society Clinical Trials Group (ANZICS CTG). The study has been endorsed by the ANZICS CTG. The principal publication from the study will be authored as "The PHARLAP Study Investigators for the ANZICS CTG". This will be on behalf of the writing committee and all PHARLAP Investigators with full credit being assigned to all collaborating investigators, research coordinators and institutions. Where an individual's name is required for publication it will be that of the writing committee, with the chair of the writing committee listed first and subsequent authors listed alphabetically.

Funding bodies will be acknowledged in the publication.

Other manuscripts and sub-studies may be authored differently but these must follow the conditions of ANZICS CTG endorsement and be approved by the PHARLAP MC. This may lead to manuscripts authored by a list of individual authors on behalf of the PHARLAP Study Investigators for the ANZICS CTG.

PROJECT TIMELINE

Timeframe Indicator	Milestone
January 2011	ANZICS CTG endorsement
April 2011	NHMRC funding application submitted
August 2011	Alfred Hospital funding application successful
October 2011	NHMRC funding application successful
November 2011	Commencement of study organisation

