There is substantial experimental evidence, biological rationale, and supportive clinical evidence to suggest the efficacy of the PHARLAP ventilation strategy in ARDS. However, mostly because of concern that SRM's and high PEEP may cause barotrauma and haemodynamic instability in critically ill patients, previous trials may have been sub-optimally designed to determine the true efficacy of such an OLS. The PHARLAP strategy is more intensive, more individual patient tailored and at least as safe as previously studied open lung strategies. In addition, the PHARLAP strategy can be delivered by almost any clinician using any conventional mechanical ventilator and if proven effective and safe, would be highly applicable for widespread use (including the developing world). Given the significance and cost of ARDS, the possible benefits of this strategy, the growing number of recommendations for the use of a LRM with elevated levels of PEEP^{18,19,46}, this study is an important undertaking. The trial will determine whether the PHARLAP ventilation strategy is effective in increasing ventilator free days in patients with ARDS. If the PHARLAP strategy is proven to improve ventilator free days it will provide a strong impetus to conduct an international phase III RCT to determine the effects of this strategy on mortality.

OBJECTIVES

Aim

To determine the efficacy of the PHARLAP strategy compared to a control ventilation strategy in increasing ventilator free days assessed during the 28 days post randomisation.

Hypothesis

The PHARLAP strategy group will have a higher number of ventilator free days at day 28 than the control group.

STUDY OUTCOME MEASURES

Primary outcome

- Number of ventilator free days at day 28 post randomisation

Secondary outcome

- Physiological outcomes:
 - PaO₂/FiO₂ ratio
 - Static lung compliance
- Inflammatory outcomes:
 - Baseline to day 3 change in IL-8 and IL-6 concentrations in broncho-alveolar lavage fluid
 - Baseline to day 3 change in IL-8 and IL-6 concentrations in plasma
- Clinical/patient-centred efficacy outcomes:
 - Use of rescue therapies for severe hypoxaemia – inhaled nitric oxide, inhaled prostacyclin, prone positioning, high frequency oscillatory ventilation and extracorporeal membrane oxygenation (ECMO)
 - Incidence of acute kidney injury (AKI)
 - ICU and hospital length of stay
 - Quality of life assessment (SF-36v2 and EQ-5D) at 6 months
 - Mortality at ICU/hospital discharge, 28 days, 90 days and 6 months

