 - Cause of death
- Safety outcomes:
 - Barotrauma
 - Severe hypotension
 - Serious adverse effects (SAEs)
- Economic outcomes:
 - Cost effectiveness analysis at 6 months (based on EQ-5D)

Determination of primary outcome

The primary outcome is the number of ventilator free days at day 28 post randomisation, and will be defined as the total number of days from day 1 to day 28 on which a patient is alive and receives no assistance from mechanical ventilation, if any period of ventilator liberation lasts at least 48 consecutive hours. Study day 1 is the day of enrolment and will continue until the end of the daily ICU chart used at that site, or the end of the calendar day if electronic data collection systems are used. If patients are on mechanical ventilation for any portion of the study day they will be classified as being on mechanical ventilation for that entire study day. To be considered truly liberated from mechanical ventilation, the patient will need to have at least 48 consecutive hours where they are liberated from mechanical ventilation. This means that if, for example, they have 47 consecutive hours liberated from mechanical ventilation and then receive mechanical ventilation, none of this time will be considered as ventilator free. But if, for example, they have 49 consecutive hours liberated from mechanical ventilation and then receive mechanical ventilation, all of this time will be considered as ventilator-free, to contribute to classification of the ventilator-free status for each study day. Non-invasive mechanical ventilation will not be considered assistance if it is provided by face or nasal mask, but will be considered assistance if it is provided by tracheostomy. Any patient who dies before weaning from mechanical ventilation will be allocated the value of 0 ventilator free days. Any patient who dies after weaning from mechanical ventilation (ie. they have at least 48 consecutive hours off mechanical ventilation) but before day 28 will not have the days after their death until day 28 considered as a ventilator free day.

STUDY METHODOLOGY

Study outline

A phase II, multi-centre, prospective, randomised controlled trial.

Study population

Patients meeting all the inclusion and none of the exclusion criteria in the ICU will be eligible for enrolment.

Inclusion criteria

Adult ICU patients who meet all of the following criteria:

- Currently intubated and receiving mechanical ventilation

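### ICU and hospital length of stay are compared as efficacy outcomes with no rule for deaths, so if patients who die have shorter stays, a mortality difference pushes the comparison the wrong way

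*Combined protocol and SAP*

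**What the plan says.** Under Study Outcome Measures, the secondary outcomes headed "Clinical/patient-centred efficacy outcomes" include "ICU and hospital length of stay". No starting point, time window or treatment of deaths is given. The pilot trial section counts the pilot's result on stay among its non-significant improvements, so shorter stay is meant to be better.

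The Statistical and analytical plan has no sentence on length of stay. Its general rule applies: Student's t-test for normally distributed continuous variables and "Wilcoxon rank-sum tests for non-normally distributed continuous variables". It adds "All analyses will be intention-to-treat", so patients who die are included.

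Death is handled for two other outcomes:
- Ventilator-free days: "Any patient who dies before weaning from mechanical ventilation will be allocated the value of 0 ventilator free days".
- Duration of ventilation: "Duration of ventilation will be analysed using Cox-Proportional Hazards regression with deceased patients censored at death", and in addition "duration of ventilation will be stratified into survivors and non-survivors".

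Neither provision is extended to length of stay. Mortality is a separate secondary outcome: "Mortality at ICU/hospital discharge, 28 days, 90 days and 6 months". A complete SAP is promised before study completion, but no text from it on stay is in the documents.

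**The concern.** A stay ends at discharge or at death. With no further rule, a death in ICU on day 4 is a four-day stay, ranked beside the fastest recoveries. The scale then means opposite things for the two kinds of patient: short is good for a survivor and bad for a patient who dies.

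If deaths tend to have the shorter stays, an arm that prevents deaths swaps some short stays for longer ones and can look worse although no survivor stays longer. An arm that causes early deaths can look better. The second error matters here because the protocol acknowledges concern about barotrauma and haemodynamic instability with this type of strategy. The plan guards against this problem for ventilator-free days and addresses death for duration of ventilation, so the gap for stay looks like an omission rather than a choice.

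**Working it through.** **1. The plan's own figures.** None is stated for length of stay. The enrolment figure supplies the arm size. A difference of one third of an SD, two-sided 0.05 and 80% power needs 142 per arm, 284 in all, against 282 stated. Then 282 × 1.15 = 324.3 and 324 × 1.05 = 340.2. Enrolling 340 with equal allocation gives 170 per arm. This calculation is not in question.

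**2. What the documents offer on stay and death.** Background & Rationale gives mortality of 34% (late-1990s survey) and 22% at day 28 (6 of 27 patients, 2010). In the 2010 study 10 of the 27 were still in hospital at day 28, so 27 − 6 − 10 = 11 had left alive. Counting stay from the start of that follow-up, all 6 deaths had shorter hospital stays than those 10 patients. That settles 6 × 10 = 60 of the 6 × 21 = 126 pairs of a death and a day-28 survivor (48%). The other 66 pairs are unknown, as are later deaths among the ten. This makes shorter stays in deaths plausible for hospital stay but does not establish them.

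**3. Assumptions.** Log-normal stays with log-SD 0.7; survivor median 25 days; median stay in deaths varied from 8 to 25 days; stay distributions the same in both arms, so treatment changes mortality only.

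**4. Shift in mean stay.** Difference = (difference in mortality) × (mean survivor stay − mean stay in deaths), where mean = median × exp(0.7²/2) = median × 1.278. For medians 25 and 8 and mortality 30% v 22%: 0.08 × (31.9 − 10.2) = 1.7 days longer in the better arm.

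**5. Effect on the Wilcoxon test.** Let θ be the probability that a survivor's stay exceeds that of a patient who dies: θ = Φ[ln(25/m) / (0.7√2)], with m the median stay in deaths. The probability that a patient in the better arm has the longer stay is 0.5 + (θ − 0.5) × (difference in mortality). Its null standard error is √[(2n+1)/(12n²)] = √[341/(12 × 170²)] = 0.0314. With z the excess over 0.5 divided by that error, the chance of a significantly longer stay is about Φ(z − 1.96).

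Worked case, m = 8: θ = Φ(1.139/0.990) = 0.875; excess = 0.375 × 0.08 = 0.030; z = 0.957; Φ(−1.00) = 0.158.

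| Mortality, control v PHARLAP | Medians, survivors/deaths (days) | θ | z | PHARLAP significantly longer |
|---|---|---|---|---|
| 30% v 22% | 25/8 | 0.875 | 0.96 | 15.8% |
| 30% v 22% | 25/12 | 0.771 | 0.69 | 10.2% |
| 30% v 22% | 25/16 | 0.674 | 0.44 | 6.5% |
| 30% v 22% | 25/25 | 0.500 | 0 | 2.5% (chance) |
| 22% v 17% | 25/8 | 0.875 | 0.60 | 8.7% |
| 30% v 22% (ICU) | 12/8 | 0.659 | 0.41 | 6.0% |
| 30% v 22% (ICU) | 14/7 | 0.758 | 0.66 | 9.7% |

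Simulation agrees: about 16%, 10%, 6% and 2.5% for the first four rows, about 8% for the fifth, and about 5–9% for the ICU rows.

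**6. The opposite error.** With medians 25/8 and mortality raised from 22% to 30%, the arm with more deaths has significantly shorter stay in about 15% of simulated trials.

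**7. Equal or longer stays in deaths.** With log-SD 0.8, mortality 34% v 24% and survivor median 14 days, a median of 14 days in deaths gives 2.8% worse and 2.4% better, which is chance. A median of 20 days reverses the bias: 0.6% worse, 5.9% better.

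**8. What free days would show.** In the 25/8 simulations, hospital-free days to day 90 (death = 0) favour the better arm by 4.8 days at 30% v 22% and 3.0 days at 22% v 17%. Dividing by the mortality differences, 4.8/0.08 = 60 and 3.0/0.05 = 60: each prevented death adds about 60 days. The gain comes wholly from mortality.

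**The case against.** The strongest objection is that the size rests on stays the documents do not report. This stands. The bias fades to chance as the two medians meet and reverses if deaths stay longer, so only a range can be given.

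The second is that a reader is protected. The primary outcome scores death before weaning as 0, and mortality is reported at several times, so a survival difference would be visible beside length of stay. This stands in part. It limits the risk of misreading, but the listed comparison still mixes recovery with death.

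The third is that the promised SAP may deal with the matter. It may, but a promise is not a rule.

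The fourth is that free days are a composite, and that a survivor/non-survivor split or a competing-risk analysis would be a smaller change. It is true that free days partly repeat the mortality outcome. However, a survivors-only comparison conditions on something that happens after randomisation, and censoring at death treats a patient who has died as still able to be discharged. The split is better used descriptively.

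A reader might also infer that the protocol expects mortality to fall from 34% to 22%, which would give wrong-direction significance in about 30% of trials with the 25/8 medians. The documents do not support that. The two rates come from separate background surveys, the sample-size section states no mortality assumption, and effects on mortality are left to a later phase III trial.

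**Conclusion.** The concern holds as a gap in the analysis of a secondary outcome. As written, length of stay is compared in all randomised patients with no rule for deaths, so an early death counts as a short stay.

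The direction of bias depends on patients who die having shorter stays than survivors, and its size also depends on the mortality difference. For hospital stay at 30% v 22% mortality and a survivor median of 25 days, the better arm is significantly worse in 16% of trials down to 2.5%, the chance level, as the median stay in deaths rises from 8 to 25 days. At 22% v 17% with 25/8 days it is about 8%. A strategy that raised mortality from 22% to 30% would look significantly better on stay in about 15%. All these figures are illustrations under stated assumptions.

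Three stronger readings are not supported. The hospital-stay figures cannot be carried over to ICU stay, where the assumed medians give about 5–9%. The direction is not certain. With equal mortality and no effect on stay there is no bias. The primary analysis and the sample size are unaffected.

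**What to change.** In Study Outcome Measures and in the Statistical and analytical plan:

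- Make the between-arm comparison on ICU-free days to day 28 and hospital-free days to day 90, both counted from randomisation, with death by that day scored 0.
- Report raw ICU and hospital stay descriptively only, overall and split by survivors and non-survivors, as the plan already does for duration of ventilation.
- Confirm that the case report form records ICU and hospital discharge dates, and readmissions up to each cut-off. The data list names length of stay, survival and discharge destination, and the schedule of events has survival status at ICU and hospital discharge, day 28 and day 90. Dates and readmissions are not named.

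The cost is outcome and SAP wording plus that check. The downside is that free days combine stay with mortality and are less familiar than days of stay, so they must be read beside the separate mortality outcome.

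### The ventilator-free-day score lets a patient who dies by day 28 keep free days and outrank a survivor, and no planned analysis scores every such death as 0

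*Combined protocol and SAP*

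**What the plan says.** The protocol's section on determination of the primary outcome counts study days 1 to 28 "on which a patient is alive and receives no assistance from mechanical ventilation". These days are credited provided that at least one spell off the ventilator reaches 48 hours without a break. A day with any ventilation counts as a ventilated day. Mask support does not count against the patient: "Non-invasive mechanical ventilation will not be considered assistance if it is provided by face or nasal mask".

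Deaths fall under two rules:

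- "Any patient who dies before weaning from mechanical ventilation will be allocated the value of 0 ventilator free days".
- A patient who dies after weaning but before day 28 "will not have the days after their death until day 28 considered as a ventilator free day". Weaning here means only this: "ie. they have at least 48 consecutive hours off mechanical ventilation". The reason for stopping ventilation plays no part.

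The statistical and analytical plan does not name a test for VFDs. It prescribes "Wilcoxon rank-sum tests for non-normally distributed continuous variables", and the sample-size section expects VFDs to be non-normal, so the rank-sum test is the likely primary test. Mortality at 28 days and cause of death are secondary outcomes. Duration of ventilation is analysed by a Cox model with deaths censored, and separately in survivors and non-survivors. A complete SAP is to be finalised before study completion. Under Significance, the protocol says that if VFDs improve, "it will provide a strong impetus to conduct an international phase III RCT to determine the effects of this strategy on mortality".

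**The concern.** VFDs are used to combine survival and liberation in one number, and a rank test needs the order of that number to make sense. Under this rule a death takes the lowest score only if it comes before 48 hours off the ventilator. Otherwise the score reflects how long the patient lived after liberation, and it can exceed that of a living patient.

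The score therefore depends partly on when and why ventilation was stopped. Treating staff deliver visibly different strategies, and the only blinding described is that of the laboratory scientists. The supplied text has no rule for extubation for comfort care. If post-liberation deaths are more common or later in one arm, VFDs can differ at equal mortality, or can understate harm when mortality is higher in one arm. A VFD result is meant to motivate a mortality trial, so the second possibility is the more serious.

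**Working it through.** **Plan's own figures.** At 1/3 SD, 80% power and two-sided 0.05, n per arm = 2 × (1.960 + 0.842)² / (1/3)² ≈ 141.3. That is 142 per arm or 284 in total, against the stated 282. Then 282 × 1.15 = 324.3, and 324 × 1.05 = 340.2. The implied SD is 3/0.33 ≈ 9.1 VFDs. The calculations below use 324/2 = 162 per arm.

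**Worked scores** (the text does not say whether the day of death counts, so both values are given where they differ):

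| Patient | VFDs |
|---|---|
| Last ventilated day 4, dies day 26 | 21 or 22 |
| Survivor, last ventilated day 10 | 18 |
| Survivor, still ventilated day 28 | 0 |
| Comfort extubation day 5, dies day 9 | 3 or 4 |
| Dies on the ventilator, never weaned | 0 |

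The first patient outranks both survivors.

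**Inputs for size.** The background section gives 22% mortality at day 28 (6 of 27) and 34% from an older survey without a stated time point; 28% is the midpoint. The following are assumptions:

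- Allocation is 1:1.
- Liberation times in survivors are lognormal with median 9 days and log-SD 0.6, which gives a mean of about 17 VFDs in survivors.
- The share of deaths credited is 10% to 50%.
- Credited days average about 9 for patients liberated who die later, or 1–4 (mean 2.5) for comfort extubation.

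**Equal mortality.** Gap = mortality × difference in share credited × mean days credited.

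| Shares credited | Days credited | Gap (VFD) | Rank-test rejection |
|---|---|---|---|
| 10% v 30% | 2.5 | 0.28 × 0.20 × 2.5 = 0.14 | about 6% |
| 10% v 30% | 9 | 0.28 × 0.20 × 9 = 0.50 | about 7–8% |
| 10% v 50% | 2.5 | 0.28 × 0.40 × 2.5 = 0.28 | about 8–9% |
| 10% v 50% | 9 | 0.28 × 0.40 × 9 = 1.01 | about 13–15% |
| Equal shares | either | 0 | about 5% |

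Rejection rates come from 3,000–4,000 simulated trials. With every death by day 28 scored 0, the gap is about 0 and rejection is 4–6% in every row. In patient numbers, 28% of 162 is about 45 deaths per arm, so 10% v 30% means roughly 5 v 14 credited deaths. A credited death outranks about 14–16% of survivors at about 9 days, and about 4% at 1–4 days.

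**Unequal mortality, 36% v 28%, with 40% v 10% of deaths credited:**

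- Deficit with death = 0: 0.08 × 17 = 1.36 VFD.
- Credit at 9 days: 0.36 × 0.40 × 9 − 0.28 × 0.10 × 9 = 1.30 − 0.25 = 1.04. The remaining deficit is about 0.3, and rejection falls from about 23–25% to about 6–7%.
- At 6 days, in a separate model set to a mean of 11.8 VFDs (the lower pilot mean) and run at baseline mortality of 22% and 34%, a deficit of 1.2–1.5 shrinks to about 0.6.
- At 2.5 days: 0.36 × 0.40 × 2.5 − 0.28 × 0.10 × 2.5 = 0.29. The remaining deficit is about 1.1.

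**The case against.** The strongest reply is that this is a stated convention and not an error. The rule is explicit, covers each type of death, and agrees with its own definition of a free day. That stands: nothing in the text contradicts it. Scoring every death as 0 has its own cost, because a patient who is truly liberated and later dies of another cause loses all credit.

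The plan also has partial safeguards: 28-day mortality, cause of death, and duration of ventilation split by survival. These would help a careful reader see where a VFD difference came from. None of them analyses VFDs with deaths scored 0, and the Cox model censors deaths, so it does not treat death as the worst result either.

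A reader might infer three stronger things that the documents do not support:

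- **That comfort extubation by itself could materially shift the result.** It earns nothing unless the patient lives at least 48 hours afterwards. With 1–4 credited days the gap is 0.14 VFD at 10% v 30%. The larger figures describe patients who were liberated and died well afterwards.
- **That the false-positive rate is inflated.** It is not when the shares are equal. The imbalances used here are assumed, and no document reports a share or a difference.
- **That a more lethal strategy would come out ahead.** In the cases run the deficit shrinks but does not reverse. For the means to be level at 36% v 28% mortality and 9 credited days, the credited share in the worse arm would have to be (1.36 + 0.25)/(0.36 × 9) ≈ 50%, against 10% in the other.

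**Conclusion.** The concern holds as a design weakness of modest size. It follows directly from the scoring rule that a death can outrank a survivor, and that the score depends partly on decisions by staff who know the arm. Whether this biases the trial depends on a difference between arms in the share or timing of post-liberation deaths, which the documents do not quantify.

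Under the assumptions above, a moderate imbalance at equal mortality moves the result by about 5% to 17% of the 3-VFD target (0.14/3 to 0.5/3). The rule could hardly produce the target alone: every death in one arm would need on average 3/0.34 = 8.8 to 3/0.22 = 13.6 credited days, with none credited in the other. The more important consequence is masking, where a deficit of about 1.4 VFD can fall to about 0.3 under a larger imbalance and long credited survival.

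This justifies a pre-specified supporting analysis. It does not justify replacing the primary endpoint, since the 3-VFD target and the SD of about 9 are tied to the pilot data and would have to be rechecked under a new score.

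**What to change.** Keep the primary definition. In the statistical and analytical plan and the final SAP, pre-specify one key supporting analysis of the primary outcome, using the same test, in which any patient who dies on or before day 28 scores 0 VFDs whatever the ventilator status at death. Report it beside 28-day mortality by arm, and state in advance that a positive VFD result will be called robust only if this analysis agrees in direction. The SAP should also say whether the day of death counts as a free day in the primary score.

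The cost is one extra analysis and a few sentences. The schedule of events (Appendix 3) already collects survival status at 28 days, and the sample size does not change. Two limits should be acknowledged: patients truly liberated who later die of another cause lose their credit in this analysis, and a death still ties at 0 with a survivor ventilated through day 28.
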